## STATISTICS AND DATA ANALYSIS

The ultimate aim of this study is to detect differentially expressed genes triggered by the major respiratory viral pathogens (i.e. influenza virus, RSV, coronavirus) as assessed by RNA transcriptome at the time of admission that correlate with clinical outcomes. We assume that the expression of each gene is normally distributed on the log scale and that the variance is the same in the different groups and thus the only difference between the groups is the mean. At an alpha of 0.05 and at an expected standard deviation of the gene intensity measurements on the base-two logarithmic scale of 0.7 (realistic for genes that are expressed at moderate to high levels), we expect to be able to detect 90% of >2 fold differentially expressed genes (i.e. an absolute effect size of 1 on a base-two logarithmic scale) between groups of 11 patients. The calculation was based on the Affymetrix HG U133plus2 microarray platform, which contains 54,515 probe-sets. The proportions of patients recruited with each of the major pathogens (influenza virus, RSV, coronavirus) is difficult to predict following the major COVID-19 pandemic, but we anticipate that by recruiting ~100 patients, at least 11 severe and 11 non-severe patients with influenza and COVID-19 will be enrolled.

**Table 2** Power calculations

Power	Effect size in fold change		
	2	1.75	1.5
60%	5	8	15
70%	7	10	18
80%	8	12	23
90%	11	16	31
95%	13	20	38

Data and all appropriate documentation will be stored for a minimum of 10 years after the completion of the study, including the follow-up period according to Imperial College London policy.

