Using data from infection challenge models, MOSAIC and BRC-funded BioAid projects, predictive transcriptomic signatures will be identified in collaboration with the BRC Genomics Theme. Longitudinal samples and clinical data will then be used to test, validate and refine them in affected local populations. These findings will then be translated into novel diagnostic tools to assist in rational treatment decisions that will benefit both individual patients and resource allocation. Additionally, this study will establish research preparedness for upcoming pandemics and provide an on-going resource for Imperial investigators to investigate the virology and immunopathogenesis of severe respiratory viral infections, while also providing a platform for novel diagnostics and clinical management testing.

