## 1.5. Exploratory Objectives:

- Test the association between transcriptomics signatures of disease progression and clinical outcomes in adults with influenza-like illness

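### The 90% power and Table 2 are per-gene figures at an unadjusted alpha of 0.05, but they are presented as detection across 54,515 probe-sets with no genome-wide error control stated

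*Combined protocol and SAP*

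**What the plan says.** Statistics and Data Analysis opens with the purpose of the calculation: "The ultimate aim of this study is to detect differentially expressed genes triggered by the major respiratory viral pathogens". It assumes normality on the log scale and equal variances. The inputs follow: "At an alpha of 0.05 and at an expected standard deviation of the gene intensity measurements on the base-two logarithmic scale of 0.7", with this SD described as realistic for genes expressed at moderate to high levels. The claim is "we expect to be able to detect 90% of >2 fold differentially expressed genes", defined as "an absolute effect size of 1 on a base-two logarithmic scale) between groups of 11 patients". The platform behind the calculation is given as the "Affymetrix HG U133plus2 microarray platform, which contains 54,515 probe-sets". Table 2 lists patients per group for five power levels and three fold changes. From about 100 recruits the plan anticipates that "at least 11 severe and 11 non-severe patients with influenza and COVID-19 will be enrolled".

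Elsewhere the transcriptomic work is described differently. Section 1.1 says signatures will be identified from challenge studies and earlier cohorts, and then: "Longitudinal samples and clinical data will then be used to test, validate and refine them in affected local populations". Section 1.5 lists as exploratory: "Test the association between transcriptomics signatures of disease progression and clinical outcomes in adults with influenza-like illness". The primary objective (section 1.3) is descriptive.

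No section says whether the 0.05 is per gene. None names a family-wise or false-discovery-rate (FDR) method, a tolerated number of false positives, or a rule for calling a gene changed.

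**The concern.** A statement about the percentage of changed genes detected, tied to an array with a stated number of probe-sets, reads as the sensitivity of a genome-wide search. Such a search needs a threshold that allows for the number of tests. If that threshold is stricter than 0.05, power falls. If it stays at 0.05, many of the genes reported will be false.

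The plan does not say which applies, or whether the figure is meant for a single signature derived elsewhere. Because this is the only sample-size rationale, a reader cannot tell what a comparison of 11 severe with 11 non-severe patients would deliver. The calling rule could also be settled after the data are seen.

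**Working it through.** **Inputs from Statistics and Data Analysis.** Alpha 0.05; SD 0.7 on the log2 scale; 2-fold = log2 difference of 1; 11 per group; 54,515 probe-sets. Sidedness is not stated. Two-sided is inferred because only that version of the normal formula matches the table.

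**1. Reproduce Table 2.** For one test, n per group = 2(z_0.975 + z_power)² × 0.7² / (log2 FC)². For 2-fold at 90%: 2 × (1.960 + 1.282)² × 0.49 / 1 = 10.30, rounded up to 11.

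| Power | 2-fold | 1.75-fold | 1.5-fold |
|---|---|---|---|
| 60% | 4.80 → 5 | 7.37 → 8 | 14.03 → 15 |
| 70% | 6.05 → 7 | 9.28 → 10 | 17.68 → 18 |
| 80% | 7.69 → 8 | 11.80 → 12 | 22.48 → 23 |
| 90% | 10.30 → 11 | 15.80 → 16 | 30.09 → 31 |
| 95% | 12.73 → 13 | 19.54 → 20 | 37.22 → 38 |

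All 15 cells match, with no term for the number of tests. At 11 per group the power is 91.8% by the normal approximation and 89.0% by the t-test (noncentral t, 20 df, standardised difference 1/0.7).

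**2. Call genes at p<0.05.** If no gene differs, 54,515 × 0.05 ≈ 2,726 probe-sets are called. If a share p differs, the false share of calls is 0.05(1−p) / [0.05(1−p) + 0.890p]. This gives 85, 52, 34 and 18% for p = 1, 5, 10 and 20%.

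**3. Apply genome-wide control.** Assumptions: independent tests, every changed gene has the same fold change, and p is as shown. Plain Benjamini-Hochberg (BH) at level q uses the per-gene threshold a that solves a = q[(1−p)a + p × power(a)]. For q = 5% and p = 1, 5, 10, 20, 30, 50%, a = 0.000043, 0.00088, 0.0025, 0.0065, 0.0109, 0.0202.

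Power at 2-fold, 11 per group:

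| Rule | 1% | 5% | 10% | 20% | 30% | 50% |
|---|---|---|---|---|---|---|
| BH 5%, t-test | 8% | 33% | 48% | 63% | 70% | 79% |
| BH 10%, t-test | 18% | 49% | 64% | 76% | 82% | 88% |
| BH 20%, t-test | 32% | 66% | 78% | 87% | 91% | 95% |
| BH 5%, SD treated as known | 35% | 57% | 67% | 76% | 80% | 86% |

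Bonferroni (0.05/54,515 = 9.2 × 10⁻⁷) gives 0.7% by t-test. Simulated plain BH at 5% and 10% (54,515 independent genes, 20 runs each) agreed with the corresponding rows to within about one percentage point. Plain BH is slightly conservative. If the threshold is set so that the actual FDR is 5%, power is 8, 34, 50 and 67% for p = 1, 5, 10 and 20%.

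**4. What would give 90% at 2-fold?** By t-test with 11 per group, 90% power needs a = 0.0559. The share needed is p = a(1−q) / [q(0.9−a)]:
- q = 5%: 126%, so not reachable (power is about 88% even with 99.9% of probe-sets changed).
- q = 10%: about 60%.
- q = 20%: about 26%.

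**5. Larger effects.** BH at 5%, t-test, p = 1, 5, 10, 20%:
- 2.5-fold: 53, 79, 87, 93%.
- 3-fold: 83, 95, 98, 99%.
- Fold change with 90% power: 3.2, 2.8, 2.6, 2.4.

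**The case against.** The strongest reply is that the sentence is not wrong as a sensitivity. At a per-gene alpha of 0.05, the expected share of 2-fold genes declared positive is about 90%, and the plan never says this holds under genome-wide control. On that view only the false-positive criterion is missing. The first part stands and is conceded, but a reader who sees the array size beside the 90% has no means of knowing that the array size was not used.

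Other points have weight:
- **Minimum group size.** Eleven is a floor. With BH at 5% and 1, 5, 10 and 20% changed, power at 2-fold would be 72, 88, 93 and 96% with 20 per group. The plan does not promise that number.
- **Effects above 2-fold.** The claim covers these, and power for them is higher (step 5). The effect size the plan states is still a log2 difference of 1.
- **Expression filter.** The SD is tied to moderately or highly expressed genes, and a filtered set might have a larger changed share. The plan states no filter, and the table runs to 50%.
- **Fold-change cut.** Also requiring an observed 2-fold difference would leave about 44 null probe-sets instead of 2,726 (SE = 0.7 × √(2/11) = 0.298). Sensitivity at exactly 2-fold would then be about 50%. No such rule is stated.
- **Exploratory status and external signatures.** These lower the stakes and may justify a lenient FDR. They do not justify leaving the criterion open when the same section calls gene detection the ultimate aim.

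**Conclusion.** The concern holds. Table 2 and the 90% figure are per-gene power at an unadjusted two-sided 0.05, and the probe-set count plays no part in them. For genome-wide discovery with 11 per group at the stated effect size, power under BH at 5% is about 8 to 63% if 1 to 20% of probe-sets differ. It reaches 90% only with a lenient FDR, a large changed share, or both.

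That Table 2 is a single-test calculation follows from the plan's own figures. The size of the shortfall rests on assumed shares, independent tests, ordinary t-tests and one common fold change. The 0.05-level figure can apply to a single pre-specified test of a signature derived from other data, but the plan does not say that this is its use. The consequence is moderate: the primary objective is descriptive and transcriptomics is exploratory, yet this is the only justification offered for the sample size.

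**What to change.** In Statistics and Data Analysis:

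1. Name the genome-wide error-control method and its level.
2. Label the 90% figure and Table 2 as per-gene power at an unadjusted two-sided alpha of 0.05. Add power under the named method, with the assumed shares of changed probe-sets. For plain BH at 5% with t-tests, the text could read: *With 11 per group, power is 90% for changes of about 3.2-, 2.8-, 2.6- and 2.4-fold if 1, 5, 10 and 20% of probe-sets differ by that amount; for a 2-fold change it is about 8, 33, 48 and 63%.* If another method is chosen, recompute these figures.
3. State that the 0.05-level figure applies only to a single pre-specified test, such as one externally derived signature (about 89% if a standardised difference of 1/0.7 is assumed for it), and not to gene-by-gene discovery.

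The cost is wording and one added set of power figures, with no extra patients. The drawback is that the stated genome-wide power will look less favourable.

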## REGULATORY ISSUES

### 1.17. Ethics approval

The Study Coordination Centre has obtained approval from the Essex Research Ethics Committee (REC) and Health Research Authority (HRA). The study must also receive confirmation of capacity and capability from each participating NHS Trust before accepting participants into the study or any research activity is carried out. The study will be conducted in accordance with the recommendations for physicians involved in research on human subjects adopted by the 18th World Medical Assembly, Helsinki 1964 and later revisions.

### 1.18. Consent

Consent to enter the study will be sought from each participant only after a full explanation has been given, an information leaflet offered, time allowed for consideration, and any questions participants may have answered. Signed participant consent will be obtained prior to any screening tests being carried out. The right of the participant to refuse to participate without giving reasons must be respected. All participants are free to withdraw at any time from the protocol treatment without giving reasons and without prejudicing further treatment.

### 1.19. Confidentiality

The Chief Investigator and all of the research team will preserve the confidentiality of participants taking part in the study and abide by the Data Protection Act. All personal/identifying information will be stored in password protected files, accessed via on password protected computer accounts. Only the study research nurses and doctors will have access to this information. PID (Personal Identifiable Data) will be stored for 10 years as per College retention policy. Paper medical records will be stored as per Trust policy, within a key-coded and fireproof door medical records storage facility within the ICRF. The site file and paper CRFs will be kept in a locked filing cabinet, in a locked office within the Commonwealth building at Hammersmith campus. The investigators will adhere to the GDPR and Imperial College London policies (UK Policy Frame Work for Health and Social Care Research) for handling any data.

#### Indemnity

Imperial College London as sponsor of this study holds negligent and non-negligent harm insurance policies which apply to this study.

#### Sponsor

Imperial College London will act as the main sponsor for this study. Delegated responsibilities will be assigned to the NHS trust taking part in this study.

#### Funding

This study is funded by the NIHR Imperial Biomedical Research Centre (BRC). They are acting as sole funders and this agreement is in place. The investigators will not receive any additional payment above their normal salaries. Participants in the study will have be compensated £50 on the Day 28 visit due to the time and inconvenience taken. If they do not complete the out-patient visit, this donation is not applicable.

### 1.20. Audits and inspections

The study may be subject to inspection and audit by Imperial College London under their remit as sponsor and other regulatory bodies to ensure adherence to GCP and the NHS Research Governance Framework for Health and Social Care (2nd edition).

## 1.29. Sample storage and usage

Samples of tissue, cells and fluids will be stored at the Commonwealth building and Medical School building sites at Imperial College London. Samples will be pseudonymised. These may be used for further assays or in other ethically approved studies. Samples and data may be shared with UK and international collaborators in studies that have been approved by local ethics committee and subject to a valid Materials Transfer Agreement. Data and samples sent outside the UK will be pseudonymised with no patient identifiable data transferred.

## STUDY MANAGEMENT

The day-to-day management of the study will be co-ordinated through [name], Clinical Senior Lecturer and Honorary Consultant in Infectious Diseases. In addition, a safety monitoring committee will convene monthly during the study to discuss all adverse events, protocol deviations, and other safety issues.

## PUBLICATION POLICY

Our expectation is that after analysis the data from this study will be widely distributed in the medical and scientific community. Facilitated with presentations at local, national and international meetings, we hope to publish widely in the medical literature. In addition we have an excellent media department at Imperial College and will publicise research that has public interest when it is published. No identifying participant information will be published. The study will be registered on clinicaltrials.gov.

